Primary and secondary outcomes:	
A) Practicability of intervention
 
 ▪ Estimation of time / cost of intervention including training for GPs and medical assistants 
B) Feasibility of trial
 
 ▪ Reasons for non-participation of patients ▪ Proportion of patients with loss to follow up compared to entire population ▪ Feasibility of taking measurements T0, T1 (Time required by GP and medical assistant for documentation, content and duration of patient interviews) 
C) Test potential outcome criteria for the main trial:
 
 1. Appropriateness of medication (potential primary outcome criterion in the main trial): the appropriateness will be rated by two experts independently and blinded with regard to the group to which the patient belongs by means of the Medication Appropriateness Index (MAI) and selected scales from the PiDoc®-classification system. The feasibility (quantity of trial data required, time consumed by medication review) will be checked and the effect size of the intervention will be calculated before and after, as well as between groups. 2. Medication complexity: 
 ▪ Sum of prescriptions ▪ Number of single doses / day ▪ Complexity of the medication regimen (Medication Regimen Complexity Index, MRCI) 3. Adherence and other factors 
 ▪ Adherence as observed from discrepancies between intake (patient interviews) and the prescription (doctor's documentation) at T0, T1 and T2. 
 - Discrepancy score, DIS (Sum of all discrepancies in medicine, time of intake, frequency and dose / sum of all prescriptions, DIS >0.2=1 - Overestimate/Underestimate of actual intake by doctor: Drug Score (DS, Sum of all drug intake / sum of all prescriptions) DS<0.8 or DS>1.2=1. - Dose Score (DoS): $DoS = d1(a1) + d2(a2) + d3(a3) + \dots / n$ d = patient's intake (0.1) of prescribed medicines, n = sum of all prescriptions, a = variance (actual dd intake/prescribed dd); DoS<0.8 or DS>1.2=1. - Regimen Score (RS): $RS = d1(b1) + d2(b2) + d3(b3) + \dots / n$ d = patient's intake (0.1) of prescribed medicines, n = sum of all prescriptions, b = variance (actual intake frequency per day / prescribed frequency per day); RS<0.8 or DS>1.2=1. ▪ Self reported adherence of patients (Medication Adherence Report Scale, MARS and adherence according to Morisky) ▪ Attitude of patients to medicinal therapy (Beliefs about Medicines Questionnaire, BMQ)

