4.1.2 Secondary outcomes

Secondary outcomes are:

1) *Change in MAI score after 12 weeks*

- Difference between base value (T0) and value after 12 weeks (T2)

2) *Change in complexity of medication after 6 and 12 weeks*

- Total number of prescriptions
- Number of single doses / day
- Medication regimen complexity (Medication Regimen Complexity Index, MRCI)

3) *Change in adherence and associated variables*

- Observed adherence measured as the difference between intake (*brown bag review*) and prescribed medication (physician's records) after 6 to 12 weeks.
 - o Discrepancy score, DS (Sum of all differences in drug, time of intake, frequency and dose) / Sum of all prescriptions, $AS > 0.2 = 1$
 - o Overestimate / underestimate of actual intake by the doctor:
Drug Score (DS, Sum of all drugs taken/sum of all prescriptions), $DS < 0.8$ oder $DS > 1.2 = 1.31$
 - o Dose Score (DoS)
 $DoS = d1(a1) + d2(a2) + d3(a3) + \dots / n$

d = Patient intake (0.1) of prescribed medication

n = Sum of all prescriptions

a = Discrepancy rate (actual intake dd / prescribed dd)

DoS<0.8 or DS>1.2=1.31

o Regimen Score (RS)

RS = d1(b1) + d2(b2) + d3(b3) + ... /n

d = Patient intake (0.1) of prescribed drugs

n = Sum of all prescriptions

b = Discrepancy rate (actual frequency of intake per day / prescribed frequency of intake per day)

RS<0.8 oder DS>1.=1.31

- Change in reported patient adherence (Medication Adherence Report Scale, MARS) *after 6 and 12 weeks*
- Change in the attitude of patients to medicinal therapy (Beliefs about Medicines Questionnaire, BMQ) *after 6 and 12 weeks*
- Change in patient satisfaction with information received on medicines *after 6 and 12 weeks*

4) *Change in quality of life and maintenance of functional status after 6 and 12 weeks*

- Change in general quality of life (EuroQuoL)
- Change in or maintenance of functional status in accordance with WHO Disability Assessment Schedule (WHO-DAS II)

5) *Change in intensity of pain after 6 and 12 weeks*

- Verbal rating scale (VRS)

6) *Days in hospital for whatever reason*

7) *Death for whatever reason*

8) *Adverse drug reaction (ADR)*

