9.3.6.1 Medication

Long-time medication and OTC drugs (trade name, National Drug Code, dose, prescribed by whom, duration of intake more or less than three weeks) currently being taken, acute medication, including OTC drugs (in case of what symptoms, single dose, total maximum dose) autonomous preparation and intake of medication vs. support from third parties, known allergies, adverse drug reactions.

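### The Dose and Regimen Scores let under- and over-intake cancel, and the all-prescriptions denominator, read literally, counts unused as-needed drugs as omissions

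*Protocol*

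**What the plan says.** Section 4.1.2, and the synopsis in 1.4 with small differences of wording, define four scores for observed adherence. All four are divided by the number of all prescriptions.

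- The Discrepancy Score counts differences in drug, time, frequency and dose, and is coded 1 above 0.2. It is called DIS in 1.4, and that label is used here.
- The Drug Score is "Drug Score (DS, Sum of all drugs taken/sum of all prescriptions", under a heading about the doctor's over- or underestimate of intake.
- The Dose Score sums d times a over the drugs and divides by n, with "d = Patient intake (0.1) of prescribed medication", "a = Discrepancy rate (actual intake dd / prescribed dd" and "n = Sum of all prescriptions". The synopsis has the same ratio: "n = sum of all prescriptions, a = variance (actual dd intake/prescribed dd".
- The Regimen Score replaces a by "b = Discrepancy rate (actual frequency of intake per day / prescribed frequency of intake per day".

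The Dose Score cut-off is printed as "DoS<0.8 or DS>1.2=1.31". I read it as coded 1 below 0.8 or above 1.2, with the label DS in the upper limit a slip and the trailing 31 a reference mark. The printed 0.1 for d is read as 0 or 1.

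Neither section says whether as-needed prescriptions count. The case report form (9.3.4.3) records current medication without limiting it to long-term drugs. The telephone interview (9.3.6.1) asks separately about "acute medication, including OTC drugs (in case of what symptoms, single dose, total maximum dose".

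**The concern.** There are two separate weaknesses in how the scores are built.

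First, a mean of ratios around 1 measures net deviation. A drug not taken contributes 0 and a drug taken at twice the dose contributes 2, so the two together look like two drugs taken correctly. DS has a related gap: its numerator is not limited to prescribed drugs.

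Second, an as-needed drug has no prescribed daily dose or frequency, so a and b cannot be formed for it. If it is on the doctor's list and is rightly not used, it adds 1 to the denominator and 0 to the numerator, and an exactly adherent patient moves towards the lower cut-off.

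The parameters in 3.2 are collected to identify further target variables for the main trial. A score that misses gross errors, or that depends on how many as-needed entries are on the list, could mislead that choice.

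**Working it through.** The protocol gives formulas and cut-offs but no numerical result for these scores, so there is no figure to reproduce. The formulas are applied to example patients.

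**Inputs.** Formulas and cut-offs are from 1.4 and 4.1.2. The minimum of five long-term drugs is from 6.3.1, with long-term drugs taken here as scheduled. The number p of unused as-needed prescriptions is not in the document and is varied as an assumption.

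**Formulas.** DS = drugs taken / n. DoS = sum(d × a) / n. RS = sum(d × b) / n. DIS = discrepancies / n, with each error counted once.

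**Check.** Five drugs, all taken as prescribed: DS = DoS = RS = 5/5 = 1.0 and DIS = 0/5 = 0. All are coded 0, as they should be.

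**Cancellation (no as-needed drugs involved)**

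| Patient | DoS | DS | DIS |
|---|---|---|---|
| 5 drugs: 1 omitted, 1 doubled | (1+1+1+2+0)/5 = 1.0, coded 0 | 4/5 = 0.80, coded 0 | 2/5 = 0.40, coded 1 |
| 5 drugs: 2 omitted, 2 doubled | (1+2+2+0+0)/5 = 1.0, coded 0 | 3/5 = 0.60, coded 1 | 4/5 = 0.80, coded 1 |
| 6 drugs: 3 at half, 3 at 1.5 times | (1.5+4.5)/6 = 1.0, coded 0 | 6/6 = 1.0, coded 0 | 6/6 = 1.0, coded 1 |
| 10 drugs: 1 omitted, 1 doubled | (8+2+0)/10 = 1.0, coded 0 | 9/10 = 0.90, coded 0 | 2/10 = 0.20, coded 0 |

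RS equals DoS when the change is in frequency. If only the dose is doubled in the first row, RS = 4/5 = 0.80, still coded 0.

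**Offsetting in DS.** In the second row DS is 0.60, coded 1. If that patient also takes two unprescribed drugs and they count as taken, DS = (3+2)/5 = 1.0, coded 0.

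**As-needed drugs in the denominator.** For s scheduled drugs taken exactly and p as-needed drugs not used, DS = DoS = RS = s/(s+p). This is below 0.8 when s < 4p. If non-use counts as a discrepancy, DIS = p/(s+p), which exceeds 0.2 under the same condition.

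| p (assumed) | Condition | Eligible patients miscoded | Example |
|---|---|---|---|
| 1 | s < 4 | none, since s is at least 5 | 5+1: 5/6 = 0.833, DIS 1/6 = 0.167, coded 0 |
| 2 | s < 8 | s = 5 to 7 | 6+2: 6/8 = 0.75, DIS 2/8 = 0.25, coded 1 |
| 3 | s < 12 | s = 5 to 11 | 8+3: 8/11 = 0.727, DIS 3/11 = 0.273, coded 1 |

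At 8+2 the scores are exactly 0.80 and 0.20, so nothing is flagged. Taking the two unused entries off the 6+2 list moves DS, DoS and RS from 0.75 to 6/6 = 1.0 with no change in intake.

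**After the change proposed below.** The 6+2 patient scores 1.0 on DS, DoS and RS and 0 on DIS. The share of drugs whose own ratio is outside 0.8 to 1.2 is 2/5 = 0.40 in the first cancellation row, which is flagged. In the ten-drug row it is 2/10 = 0.20, which is not above 0.2. That patient stays unflagged because of the tolerance, not because the errors cancel.

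**The case against.** The strongest reply is that the protocol never says as-needed drugs belong in the denominator. Its mentions of such drugs are on the intake side: the home medication entered in step 4 of 8.1, and the telephone interview, which already separates acute from long-term drugs. Section 12.2 leaves detail to a statistical analysis plan that is not at hand, and such a plan could exclude drugs without a prescribed daily dose. This stands in part. Inclusion is the literal reading of all prescriptions, not an explicit rule, and the miscoding depends on an assumed count. But the protocol does fix the denominator, so a plan that excluded these drugs would be amending it.

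A reader might infer that every score codes a patient with omitted and doubled drugs as adherent. The document does not support that: DIS does not cancel, and it flags three of the four example patients.

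A reader might also infer that the intervention would produce a spurious gain in adherence by clearing unused entries. Section 2.3 expects simpler regimens, and in 8.1 the GP reconciles the lists and saves a revised plan. However, no section says that unused as-needed entries are removed, and the pairs deleted in step 5 are matching ones. The effect is possible but not stated. Bringing the list into line with intake is also a real change in a quantity defined as the gap between the two.

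Finally, DS is headed as the doctor's misjudgement of intake, and code 1 is nowhere labelled non-adherent. A DS flag for a listed drug that is not taken can therefore be defended on its own terms. That does not rescue DoS and RS.

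**Conclusion.** The point holds in limited form. Cancellation in DoS and RS follows from the printed formulas without any assumption: equal numbers of omitted and doubled drugs always give DoS = 1.0, and RS = 1.0 if frequency is what doubles. DIS catches most such patients but not all. The ten-drug case passes all four scores if each error is counted once.

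The as-needed problem is conditional. It requires the literal reading of the denominator and at least two unused as-needed prescriptions. It then reaches exactly adherent patients with 5 to 7 scheduled drugs (two unused) or 5 to 11 (three unused) on DS, DoS and RS, and on DIS if non-use counts as a discrepancy. A difference between arms from this source is not established.

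These are secondary scores in a pilot whose analysis is mainly descriptive (12.2). The MAI primary outcome and N = 100 are unaffected. The correction is worth making because it is cheap and the scores are candidates for the main trial.

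**What to change.** In 1.4 and 4.1.2:

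1. Restrict numerator and denominator of DIS, DS, DoS and RS to scheduled long-term prescriptions. Identify as-needed drugs from the dosage field of the case report form or by a mark on it.
2. Count unprescribed drugs separately, so that they cannot offset an omission in DS.
3. Keep DoS and RS, described as net-deviation scores, for comparability with the cited source. Beside each, report the share of scheduled drugs whose own ratio lies outside 0.8 to 1.2, with an omitted drug counted as ratio 0. Flag a share above 0.2, in line with the DIS cut-off.

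The cost is a change of wording, one more derived variable beside each of DoS and RS and, if a mark is used, one tick box per drug. Any mark has to be in place before data collection. Restricting the denominator makes the scores somewhat less directly comparable with the cited source.

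### The upper cut-offs of the Dose Score and Regimen Score flags are set on the Drug Score, so these two flags misclassify over-intake and extra drugs

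*Protocol*

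**What the plan says.** The protocol lists four scores for observed adherence, in the synopsis (section 1.4) and again in section 4.1.2. Three matter here.

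- **Drug Score:** "Drug Score (DS, Sum of all drugs taken/sum of all prescriptions"). It is flagged when below 0.8 or above 1.2, and both limits are on DS.
- **Dose Score:** the sum over prescribed drugs of d times a, divided by n, the number of prescriptions, with "a = Discrepancy rate (actual intake dd / prescribed dd"). The flag is "DoS<0.8 or DS>1.2=1.31" in section 4.1.2 and "DoS<0.8 or DS>1.2=1" in the synopsis.
- **Regimen Score:** the same construction with "b = Discrepancy rate (actual frequency of intake per day / prescribed frequency of intake per day"). The flag is "RS<0.8 oder DS>1.=1.31" in section 4.1.2 and "RS<0.8 or DS>1.2=1" in the synopsis.

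The abbreviation list (section 16.1) gives DS as Drug Score and AS as the discrepancy score. The fourth measure, the Discrepancy Score, adds up differences in drug, time, frequency and dose, divides by the number of prescriptions, and is flagged above 0.2.

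**The concern.** DoS and RS are meant to show whether the dose and the frequency of intake match the prescription. A two-sided flag should catch both too little and too much. Here the lower side tests the right quantity and the upper side tests another one. DS counts drugs. It does not move when a patient doubles a dose, and it rises when the patient takes something that was not prescribed. DoS and RS run over prescribed drugs only, so an extra drug cannot change them.

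Two kinds of misclassification follow. Over-intake of prescribed drugs can pass unflagged, and a patient with perfect dose and frequency can be flagged because of extra drugs. In addition, the upper flag of DS, DoS and RS becomes one and the same event, DS>1.2, so three nominally separate measures would agree by construction.

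Section 3.2 says these parameters are collected to find suitable target variables for the main trial. A flag that does not measure what its name says is a poor basis for that choice.

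**Working it through.** The protocol reports no figure that depends on this rule, so there is nothing to reproduce. The check applies the stated formulas to simple patients.

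**Inputs**
- DS = drugs taken / n (synopsis; section 4.1.2).
- DoS = (sum of d × a) / n and RS = (sum of d × b) / n, reading the whole sum as divided by n and d as 0 or 1.
- Rule as written: code 1 if score < 0.8 or DS > 1.2.
- Rule with both limits on the score: code 1 if score < 0.8 or score > 1.2.
- n = 5 is the smallest number of long-term medicines allowed by section 6.3.1. n = 8 is an illustrative value.

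**Results** (score means DoS with dose ratios or RS with frequency ratios)

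| Patient | DS | Score | As written | Limits on own score |
|---|---|---|---|---|
| n = 5, all doubled | 5/5 = 1.0 | (5 × 2)/5 = 2.0 | 0 | 1 |
| n = 5, two doubled | 5/5 = 1.0 | (2 + 2 + 3 × 1)/5 = 1.4 | 0 | 1 |
| n = 8, three doubled | 8/8 = 1.0 | (3 × 2 + 5 × 1)/8 = 1.375 | 0 | 1 |
| n = 5, one omitted, three doubled | 4/5 = 0.8 | (0 + 3 × 2 + 1)/5 = 1.4 | 0 | 1 |
| n = 5 exact, plus two extra drugs | 7/5 = 1.4 | (5 × 1)/5 = 1.0 | 1 | 0 |
| n = 8 exact, plus two extra drugs | 10/8 = 1.25 | (8 × 1)/8 = 1.0 | 1 | 0 |
| n = 5, two doubled, plus two extra drugs | 7/5 = 1.4 | (2 + 2 + 3 × 1)/5 = 1.4 | 1 | 1 |
| n = 5, one doubled | 5/5 = 1.0 | (2 + 4 × 1)/5 = 1.2 | 0 | 0 |

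**Reading the table**
- A patient who takes only prescribed drugs has DS of at most n/n = 1.0. For such a patient the upper limit can never be reached, whatever the dose or frequency.
- With all prescribed drugs taken, DS exceeds 1.2 once the extra drugs exceed 0.2 × n. That is two extra drugs at n = 5 (0.2 × 5 = 1) and at n = 8 (0.2 × 8 = 1.6).
- The seventh row is flagged under both rules, but as written it is flagged for the extra drugs and not for the doubled doses.
- The last row sits exactly at 1.2 and is not flagged under either rule, so not every over-intake is affected.

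**The case against.** **This is a copy slip and the intention is evident.** The Drug Score line carries both limits on its own score, and the lower limits on DoS and RS point the same way. That is very likely right. But the slip stands in all four statements of the rule across two sections, and the protocol contains no correct version. A programmer following the text would produce the wrong flags, so the correction is still needed.

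**Over-intake is not lost.** This stands. Five drugs at double dose contribute at least five dose differences, so the Discrepancy Score is at least 5/5 = 1.0, well above its limit of 0.2. The DoS value of 2.0 is still computed; only its dichotomy is wrong.

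**The consequence is small.** This also stands. Section 12.2 makes the analysis of all result parameters primarily descriptive, with p-values of descriptive character only. The MAI outcome, the intra-class correlation and the sample size do not use these flags.

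Four stronger readings are tempting, and the document does not support them.

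- **A fully adherent patient scores 0.1.** The text has "d = Patient intake (0.1) of prescribed medication". In a protocol translated from German, where a German conjunction survives in the RS line, this is evidently 0 or 1 written with a decimal comma. Limits of 0.8 and 1.2 make no sense on any other reading.
- **DS is ambiguous.** Section 4.1.2 does label the Discrepancy Score DS, but puts its limit on AS. Section 16.1 lists DS as Drug Score, and the synopsis calls the other score DIS. The label is a slip.
- **The RS limit is unknown.** The digit missing in section 4.1.2 is supplied by the synopsis as 1.2.
- **The error differs by arm.** The intervention reconciles home and practice medication (section 8.1), which could shift DS, so a mechanism can be imagined. But the telephone interview asks about intake, including over-the-counter drugs, in both arms (sections 1.6 and 9.3.6.1), and the document gives no figure from which a difference could be derived.

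**Conclusion.** The point holds for the two binary flags. As written in the synopsis and section 4.1.2, they miss over-dosing and too-frequent intake whenever DS is at most 1.2 and the score is not itself below 0.8. They also flag patients whose dose and frequency are exact once extra drugs push DS above 1.2.

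The conclusion assumes that DS means the Drug Score, that d is 0 or 1, that the whole sum is divided by n, and that code 1 marks the out-of-range patient. The last is an inference, since the protocol does not label the codes. The number of trial patients affected cannot be estimated from the document; the examples show the direction of the error, not its frequency.

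Severity is minor: secondary, descriptive outcomes of a pilot, with over-intake still captured by the Discrepancy Score and the primary outcome unaffected. It is still worth correcting, because these measures are being screened for the main trial.

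**What to change.** In both the synopsis and section 4.1.2, state the flags as DoS<0.8 or DoS>1.2 = 1, and RS<0.8 or RS>1.2 = 1. This keeps the protocol's own limits and changes only the score that the upper limit refers to.

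As tidying in the same edit:
- restore the missing digit in the RS limit of section 4.1.2;
- print d as 0 or 1;
- use one abbreviation for the Discrepancy Score in the synopsis, section 4.1.2 and section 16.1, which now variously use DIS, DS and AS.

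The cost is wording in two sections, plus the abbreviation list if the label is harmonised. No data collection, sample size or primary analysis changes. If the flags have already been programmed, the code should be checked against the corrected rule.

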5 DESIGN AND DURATION OF TRIAL

5.1 Type and design of trial

A two armed, controlled, open cluster randomized pilot trial in the Rhein-Main region has been planned in order to achieve the aims mentioned above (compare schematic presentation in section 1.5). In the design used here groups of people rather than individuals will be allocated to the various categories (intervention vs. control). The evaluation of the Medication Appropriateness Index (MAI) will take place without knowledge of group membership.

5.2 Expected duration of trial

The recruitment of participating practices is expected to take one month as this phase will be commenced in the trial preparation phase. After the successful recruitment of practices, training for the investigators will begin and participating family doctors (investigators) made familiar with all the documents in the investigator files including the documentation requirements.

The recruitment phase for patients will not take longer than three months. Directly following the decision on the randomization status of each practice (intervention or control) the intervention practices will begin intervention training. For this purpose, the family doctors and one medical assistant per practice will take part in group training and after access to the internet-based RandomizationAiD+ has been activated also in local training with all intervention instruments incl. software functionality. Each patient (in both intervention and control groups) will be tracked for three months following successful basis documentation. Excluding evaluation, the planned duration of the trial will be around 9 months.

6 SELECTION OF TRIAL SITES AND TRIAL PARTICIPANTS

6.1 Criteria for trial sites (Family practices)

6.1.1 Inclusion criteria (Trial sites)

- Practice provides health services to persons with German statutory health insurance
- GP practice
- Physician specialises in general practice, internal medicine or has no specialist area
- Practice has internet access which can be used by medical assistant
- Investigating physician agrees to the contractual obligations of the trial
- Investigating physician agrees to train a medical assistant from the practice as part of the trial for intervention (*brown bag review*, patient interview on basis of checklist).

6.1.2 Exclusion criteria (Trial sites)

- Practice specialises in unconventional medical treatments
- Practice specialises in special indications (e.g. HIV)

